#### 9.2 Safety Reporting

Safety surveillance and safety reporting for this study are both performed by the Investigator (per the local country requirements) and starts as soon as the subject is enrolled in this study (date of signature of the informed consent). German requirements are outlined in Appendix M. Safety surveillance and safety reporting will continue until the last investigational visit has been performed, the subject is deceased, the subject/investigator concludes his participation into the study or the subject/investigator withdraws the subject from the study, except as otherwise specified in the CIP.

All reportable adverse event data including deaths and device deficiency data will be collected throughout the clinical study and will be reported to the Sponsor through the EDC system. The Investigator will record all reportable adverse events and device deficiencies on the appropriate case report forms.

Records relating to the subject's subsequent medical course must be maintained and submitted (as applicable) to the Sponsor until the event has subsided or, in case of permanent impairment, until the event stabilizes and the overall clinical outcome has been ascertained. Adverse events will be monitored until they are adequately resolved, the subject is withdrawn, or completes the study. The status of the subject's condition should be documented at each visit.

**Clinical Investigational Plan**

The Investigator will report the event to the EC per their reporting requirements.

Reportable events to Sponsor are:

1. Endpoint VARC-2 events
  - Death
  - Vascular complications
  - Stroke/TIA
  - Life threatening bleeding requiring transfusion
  - Acute kidney injury requiring dialysis
2. All Adverse Device Effects
3. All Serious Adverse Events (whether or not the event is considered device or procedure related)
4. Device deficiencies, that could have led to a serious adverse device effect
  - if either suitable action had not been taken
  - if intervention had not been made or
  - if circumstances had been less fortunate

Non-serious adverse events documentation and reporting are limited to cardiovascular and neurovascular events; they all have to be reported regardless of their relationship with the device or the procedure. All above events will be reported to the Sponsor, as soon as possible, but no later than 72 hours of first learning of the event.

The Sponsor will ensure that all events and device deficiencies are reported to the relevant authorities as per regulations.

The following information should be collected for each event:

1. Date AE occurred
2. Date the center, Investigator, became aware of the event
3. Main symptoms of the event
4. Treatment
5. Seriousness
6. Relationship to device and/or procedure
7. Status

Additional information may be requested, when required, by the Sponsor in order to support the reporting of AEs to regulatory authorities.

If required by national and local laws or regulations, the Investigator must notify the EC of the AEs reported to the Sponsor.

All adverse events will be reported as per applicable regulatory requirements.

**9.2.1 Subject Death**

All subject deaths are to be documented and reported to the Sponsor within 72 hours after becoming aware of the event.

The subject death CRF should always be accompanied with the relevant adverse event CRF and relevant source documentation. In the event of a subject death, an autopsy should be performed whenever possible and the Portico valve explanted and returned to Abbott for evaluation. Death summaries and autopsy reports should be provided to Abbott.

**9.2.2 Device Deficiency (DD)**

During the trial, the Investigator will be responsible for reporting all device deficiencies. A device deficiency is defined as an inadequacy of a medical device with respect to its identity, quality,

## Clinical Investigational Plan

durability, reliability, safety or performance and includes malfunctions, user errors and inadequate labeling.

If the device deficiency involves an adverse event, the Principal Investigator must complete an adverse event form including information on the device deficiency and report to the Sponsor within 5 days after becoming aware of the event. If the device deficiency does not involve an adverse event, then the Investigator must complete the device deficiency form within 5 days after becoming aware of the event

### 9.3 Records Retention

The Principal Investigator will maintain all clinical study documents from prior, during and (as specified) after the clinical study on file at the site for a minimum of 15 years after the termination of this study, or longer as per local laws, or when it is no longer needed to support a marketing application, whichever is later.

The PI must contact the Sponsor prior to destroying or archiving off-site any records and reports pertaining to this study to ensure that they no longer need to be retained on-site.

All original subject files must be stored for the longest possible time permitted by the regulations at the hospital, research institute, or practice in question. If archiving can no longer be maintained at the site, the Investigator will notify the Sponsor.

All data and documents will be made available on request of the relevant authorities in case of an audit.

The Sponsor will archive and retain all essential clinical study documents from prior, during and (as specified) after the clinical study as per requirements.

### 10.0 Clinical Data Handling

Overall, the Sponsor will be responsible for the data handling. The Sponsor and/or its affiliates will be responsible for compiling and submitting all required reports to governmental agencies.

Data will be analyzed by the Sponsor and may be transferred to the Sponsor's locations outside of Europe and/or any other worldwide regulatory authority in support of a market-approval application.

Abbott respects and protects personally identifiable information that we collect or maintain. As part of our commitment, Abbott is certified to the U.S. - European Union Framework Agreement regarding human resources and subject clinical trial personal information. The privacy of each subject and confidentiality of his/her information will be preserved in reports and when publishing any data. Confidentiality of data will be observed by all parties involved at all times throughout the clinical study. All data will be secured against unauthorized access.

The Principal Investigator or institution will provide direct access to source data during and after the clinical study for monitoring, audits, EC review and regulatory authority inspections. As required, the Principal Investigator or institution will obtain permission for direct access to source documents from the subject, hospital administration and national regulatory authorities before starting the clinical study.

### 10.1 Data Management Plan

A detailed Data Management Plan will be established, prior to study initiation, to ensure consistency of the data. This document will include procedures used for data review, database cleaning, issuing and resolving data queries, study/database closeout, and data export for

## Clinical Investigational Plan

statistical analysis. If appropriate, the DMP may be updated throughout the study duration. All revisions will be tracked and document controlled.

CRF data will be captured in a validated electronic database management system hosted by Abbott.

Only authorized site personnel will be permitted to enter the CRF data through the electronic data capture (EDC) system deployed by Abbott. An electronic audit trail will be used to track any subsequent changes of the entered data.

### 10.2 Document and Data Control

#### 10.2.1 Traceability of documents and data

The investigator will ensure accuracy, completeness, legibility and timeliness of the data reported to the Sponsor on the CRFs and in all required reports.

#### 10.2.2 Recording data

Source documents will be created and maintained by the investigational site team throughout the clinical study.

The data reported on the CRFs will be derived from, and be consistent with, these source documents, and any discrepancies will be explained in writing.

Required CRFs will be signed by authorized site personnel.

### 11.0 Monitoring

Monitoring will be conducted by trained and experienced clinical representatives according to the Abbott Clinical Monitoring standard operating procedure.

Prior to beginning the study, Abbott will contact the investigator or designee to discuss the study and data requirements during a site initiation visit.

After enrollment begins, a Abbott monitor will periodically review the subject records and associated source documents. Each actively enrolling site will be visited at least annually. During these routine visits, the investigator shall make subject and study records available to the clinical monitor for monitoring. There will be 100% source verification on all available source documentation. In case of a subject not being able to be located, the monitor will verify that adequate measures have been undertaken to contact the subject's treating General Practitioner and exchange data about the whereabouts and health status of the subject. Monitoring reports will be created for each visit.

Once all subjects have completed the study a close out visit will be completed.

It is the responsibility of Abbott as the Sponsor of the study to ensure the study is conducted, recorded, and reported according to the approved protocol, subsequent amendment(s), applicable regulations, and guidance documents and to secure compliance from each investigative site as necessary.

Investigators are required to adhere to the protocol, signed investigator agreement and any conditions required by the EC. If a site has long-standing, open monitoring findings or challenges with compliance, the monitor or study management shall consider developing a corrective and preventative action plan.

## Clinical Investigational Plan

### 12.0 Compliance Statement

#### 12.1 Statement of Compliance

The study will be performed in accordance with the most current versions of the World Medical Association (WMA) Declaration of Helsinki, ISO 14155 and any regional and/or national regulations and will be compliant to this International Standard and any regional and national regulations, as appropriate.

The investigator will not start enrolling subjects or requesting informed consent from any subject prior to obtaining EC approval and Competent Authority approval, if applicable, and authorization from the sponsor in writing for the study.

In case additional requirements are imposed by the EC or Competent Authority, those requirements will be followed, if appropriate. If any action is taken by an EC, and regulatory requirements with respect to the study, that information will be forwarded to Abbott.

As Sponsor, Abbott has taken up general liability insurance in accordance with the requirements of the applicable local laws. Appropriate country representative will be utilized to understand the requirements for the type of insurance that will be provided for subjects, such information will be incorporated into the informed consent, as applicable.

#### 12.2 Regulatory Inspections

The investigator and/or delegate should contact Abbott immediately upon notification of a governmental agency inspection at the site. A clinical monitor or designee will assist the investigator and/or delegate in preparing for the audit.

An investigator who has authority to grant access will permit authorized governmental agency employees, at reasonable times and in reasonable manner, to enter and inspect any establishment where devices are held (including any establishment where devices are used or where records or results are kept).

An investigator, or any person acting on behalf of such a person with respect to the study, will permit authorized governmental agency employees, at reasonable times and in reasonable manner, to inspect and copy all records relating to the study.

An investigator will permit authorized governmental agency employees to inspect and copy records that identify subjects, upon notice that governmental agency has reason to suspect that adequate informed consent was not obtained, or that reports required to be submitted by the investigator, to the Sponsor or EC have not been submitted or are incomplete, inaccurate, false or misleading.

#### 12.3 Repeated and Serious Non-Compliance

In the event of repeated non-compliance or a one-time serious non-compliance, as determined by the Sponsor, a Clinical Research Associate or clinical representative will attempt to secure compliance by one or more of the following actions:

- Visiting the Investigator
- Contacting the Investigator by telephone
- Contacting the Investigator in writing
- Retraining of the Investigator

**Clinical Investigational Plan**

If an investigator is found to be repeatedly non-compliant with the signed agreement, the CIP or any other conditions of the clinical study, the Sponsor will either secure compliance or, at its sole discretion, terminate the Investigator's participation in the clinical study.

**13.0 Core Lab**

Echocardiographic examinations will be forwarded to an echocardiographic core laboratory for interpretation. It is the responsibility of each site to perform the local interpretation of the echocardiogram for clinical assessment. The echocardiographic core laboratory will not be responsible to notify the site of any abnormal finding that are identified in the echo study.

The echocardiographic core laboratory will provide the study required interpretation and documentation of each echocardiogram submitted to the Sponsor. Data obtained from the core laboratory readings will be used for study purposes only and not for clinical treatment of the subject.

**14.0 Suspension or Premature Termination of the Clinical Investigation**

The Sponsor reserves the right to terminate the clinical investigation at any stage, with appropriate written notice to the investigators, ECs and relevant Regulatory authorities, if required.

A Principal Investigator, EC or regulatory authority may suspend or prematurely terminate participation in a clinical investigation at the investigational sites for which they are responsible. The investigators will follow the requirements specified in the Clinical Trial Agreement.

If suspicion of an unacceptable risk to subjects arises during the clinical investigation in either arm of the study or when so instructed by the EC or regulatory authority, the Sponsor may suspend the clinical investigation while the risk is assessed.

Termination criteria are set based on a maximum allowable number of major vascular complications through 30 days across the two study arms. The study will continue in the arm of the study not under suspension. The Sponsor will terminate the clinical investigation if an unacceptable risk for major vascular complications through 30 days is confirmed with accumulating data as noted in the table below. The termination criterion is selected to be  $x$  events such that the probability of observing  $x$  or more events is  $< 0.05$  assuming that the number of events follows a binomial distribution with event probability 0.119. This event probability is based on the 30-day rate of major vascular complications reported in the literature (see Section 6.3).

If the Sponsor completes an analysis of the reasons for the suspension, implements the necessary corrective actions, and decides to lift the temporary suspension, the Sponsor will inform the Principal Investigators, EC, or regulatory authority, where appropriate, of the rationale, providing them with the relevant data supporting this decision. Approval from the EC or regulatory authority, where appropriate, will be obtained before the clinical investigation resumes. If subjects have been informed of the suspension, the Principal Investigator or authorized designee will inform them of the reasons for resumption.

Number enrolled (n)	Number of events (major vascular complications through 30 days) to	Probability of observing $\geq x$ events
---------------------	--	--

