### 6.3 Sample Size

The sample size of 45 subjects for each access route is based on the desire to estimate the rate of 30-day vascular complication with a sufficient degree of precision. The rate of major vascular complications at 30 days in Portico TF EU study was 5.9%. The rate of major vascular complications reported for other TAVI valves at 30 days in a weighted meta-analysis of 3,519 patients from 16 studies ranged from 5.0% to 23.3%. The same meta-analysis calculated a major vascular complication pooled estimate 30-day rate of 11.9% (95% CI 8.6%-16.4%). Assuming an event rate of 5.9%, with 45 subjects, the exact 90% CI is (1.45%, 15.32%). Therefore, a sample size of 45 will result in the 90% confidence interval half-width of 9.42% and the 95% upper confidence limit is within the range reported in the literature

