### 6.7 Interim Analysis

No interim analyses are planned for this study.

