### 6.8 Statistical Criteria for Termination

There are no statistical criteria for termination of this study.

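### Section 14.0 sets a statistical termination rule that section 6.8 says does not exist; its table is not labelled per arm or pooled and stops at n=40

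*Combined protocol and SAP*

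**What the plan says.** Section 14.0 sets the basis of the rule: "Termination criteria are set based on a maximum allowable number of major vascular complications through 30 days across the two study arms". The next sentence reads "The study will continue in the arm of the study not under suspension". The one after it says "The Sponsor will terminate the clinical investigation if an unacceptable risk for major vascular complications through 30 days is confirmed with accumulating data" and points to a table. The limit x in that table is a count whose upper tail probability is below 0.05 under a "binomial distribution with event probability 0.119". The rate comes from the meta-analysis cited in section 6.3, which the plan describes as a "major vascular complication pooled estimate 30-day rate of 11.9" per cent.

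The table has three rows: n=20 with x=6, n=30 with x=8, and n=40 with x=9. The first column is headed only as the number enrolled, with no mention of arm or total. Section 4.2 plans at least 45 subjects in each of two access arms, so at least 90 in all.

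The statistical section reads differently. Section 6.8 states: "There are no statistical criteria for termination of this study". Section 6.7 states: "No interim analyses are planned for this study".

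**The concern.** There are two faults.

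- **Existence.** Section 6.8 denies that a statistical termination criterion exists. Section 14.0 defines one with a reference rate, a tail limit and numeric boundaries, and commits the sponsor to act on it.
- **Scope.** Within three consecutive sentences, section 14.0 counts over both arms, speaks of one arm continuing, and terminates the investigation as a whole. Two teams applying the table in good faith could count different things.

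This table is the only quantitative safety stop in the plan. The two access routes are anatomically different, so one may do worse than the other. Whether the table would respond to that depends on the point left open. The table also stops short of the planned enrolment, slightly on one reading and by more than half on the other.

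**Working it through.** **Inputs.** Reference rate 0.119, tail limit 0.05 and the three rows: section 14.0. At least 45 per arm: section 4.2. Rates of 5.9% (the earlier transfemoral Portico study) and 23.3% (top of the cited range): section 6.3. Assumptions of this review: one arm truly at 23.3%, the other at 5.9% or 11.9%, and, for the pooled reading, strict alternation of enrolment between arms. The documents give no enrolment order.

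**Step 1: reproduce the table.** P(X ≥ x) = Σ from k=x to n of C(n,k) · 0.119^k · 0.881^(n−k).

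| n | x | P(X ≥ x) | Plan | P(X ≥ x−1) |
|---|---|---|---|---|
| 20 | 6 | 0.0251 | 0.0251 | 0.0804 |
| 30 | 8 | 0.0211 | 0.0211 | 0.0584 |
| 40 | 9 | 0.0423 | 0.0423 | 0.0960 |

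Each x is the smallest count with a tail below 0.05. The arithmetic in the plan is right.

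**Step 2: subjects without a limit.** Per arm: 45 − 40 = 5 or more in each arm. Pooled, which is the literal wording: 90 − 40 = 50 or more.

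**Step 3: same data, two decisions.** Take 6 events in 20 subjects in one arm and 2 in 20 in the other. Per arm, the first arm meets its n=20 row (6 ≥ 6). Pooled, the count at n=40 is 6 + 2 = 8, below 9, so that row is not met. (The order of events decides whether an earlier pooled row was met.)

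**Step 4: chance of meeting the printed table.** This is an exact recursion over looks at n=20, 30 and 40: carry the distribution of the count forward, remove the mass at or above x at each look, and add up what was removed.

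- Table applied to the 23.3% arm alone: 0.315 + 0.133 + 0.188 = 0.636. After its first 20 subjects it is 0.315.
- Pooled, other arm at 5.9%: 0.135.
- Pooled, other arm at 11.9%: 0.292.

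Pooled n=40 holds only 20 subjects of the worse arm, so the comparison at equal exposure is 0.315 against 0.135 or 0.292. The rest of the gap up to 0.636 comes from the pooled table stopping early.

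**Step 5: carry the plan's formula on.** Smallest x with a tail below 0.05 at 0.119:

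| n | 45 | 50 | 60 | 70 | 80 | 90 |
|---|---|---|---|---|---|---|
| x | 10 | 11 | 12 | 14 | 15 | 17 |
| P | 0.0361 | 0.0308 | 0.0483 | 0.0348 | 0.0492 | 0.0357 |

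With one arm at 23.3%, the pooled table continued every 10 subjects to n=90 is met with probability 0.269 (other arm 5.9%) or 0.552 (other arm 11.9%). The per-arm table with the n=45 row reaches 0.636 + 0.048 = 0.684.

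**Step 6: false triggers at a true rate of 11.9%.**

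- Printed rows, one count (pooled or a single arm): 0.0251 + 0.0098 + 0.0219 = 0.0568.
- One arm with the n=45 row: 0.0568 + 0.0064 = 0.0632.
- At least one of two such arms: 1 − (1 − 0.0632)² = 0.122.
- Pooled, continued to n=90: 0.102.

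**The case against.** Four points on the other side have force.

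- **The arm-continuation sentence concerns suspension.** Suspension follows from suspicion of unacceptable risk in either arm, or from an instruction by the ethics committee or regulator. The table governs termination, and that sentence names the whole investigation. A reader might infer that the text requires a per-arm count. It does not: arm-level suspension beside a study-level termination count is awkward but coherent.
- **Section 6.7 does not forbid counting safety events.** A reader might infer from 6.7 and 6.8 together that the rule would never be run. The documents do not support that. Section 14.0 places the duty on the sponsor, and a safety count need not be an interim analysis. The firm conflict is between 6.8 and 14.0.
- **A missed boundary is not a missed arm.** Section 14.0 lets the sponsor suspend for suspected risk in either arm, and section 9.2 requires vascular complications to be reported within 72 hours.
- **The contrast depends on the scenario.** The 64% against 13% mixes dilution by the better arm with unequal exposure, and it uses a favourable second arm. With the other arm at 11.9% and the pooled table continued to n=90, the gap narrows to 64% against 55%. If the table was meant per arm, the loss largely disappears.

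All four stand, and they limit the size of the point. None removes the contradiction between 6.8 and 14.0, and none tells the reader which count the table uses.

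**Conclusion.** The plan is wrong as written on two counts: section 6.8 denies a criterion that section 14.0 imposes, and section 14.0 does not define what n and x count or whether termination covers one arm or the study. The table's probabilities are correct.

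With one arm at 23.3%, the chance of meeting the printed table is 64% per arm, against 13% to 29% pooled as the other arm's rate runs from 5.9% to 11.9%. These figures rest on alternating enrolment, independent events, and true rates chosen from figures in the plan. The table is silent for the last 5 or more subjects of each arm on one reading, and for the last 50 or more of 90 on the other.

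This is a weakness of the numeric rule. It does not show that the trial lacks safety oversight, nor that an unsafe arm would go unnoticed, because discretionary suspension remains.

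**What to change.** 1. **Section 6.8:** replace the denial with a reference to section 14.0.
2. **Section 6.7:** add that the section 14.0 safety count is separate from interim analysis.
3. **Section 14.0:** state whether n and x are per arm or pooled, label the table columns to match, and state whether termination applies to the arm or to the whole study. The choice is the sponsor's. A per-arm count matches the per-arm primary endpoint (4.3.1), sample size (6.3) and CE Mark analysis (6.5).
4. **Table:** carry the plan's own formula to the planned size. Per arm, add n=45 with x=10 (P=0.0361). Pooled, add n=50: 11, 60: 12, 70: 14, 80: 15, 90: 17.

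The cost is protocol wording and table rows. At a true rate of 11.9%, the chance of at least one false trigger is about 12% for two arms with the n=45 row, about 10% for the pooled table to n=90, and about 6% for the printed pooled table. The n=45 row is the least important part: by then an arm's planned minimum is already enrolled, and at 23.3% it raises detection only from 64% to 68%.

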### 5.3 Point of Enrollment

Subjects are considered enrolled in the study from the moment the subject has provided written Patient Informed Consent.

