**5.7.4 Procedural Exclusion**

During the procedure, the implanting investigator may determine transcatheter aortic valve implantation using the Portico TF or ALT Delivery System is neither feasible nor in the best interest of the subject. Any subject that does not have a delivery system enter his or her body will be withdrawn from the study. Data collected on these subjects, at baseline, will consist of reason(s) for exclusion and possible adverse events. Subjects that have a Delivery System enter his or her body but no valve will be followed for 30 days to collect adverse events.

Following the procedure, the delivery and loading systems should be securely disposed of per hospital requirements for hazardous materials. If there are any concerns noted with the delivery system, loading system, or valve during the procedure, they should be reported and returned to Abbott.

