##### 6.2.1.2 Analysis Population

All subjects who have received a Patient Information Sheet, and signed an Informed Consent Form and Data Protection Form will be considered enrolled in the study. However, the analysis population will be based on subjects who have provided signed Informed Consent Form and Data Protection Form and had the SJM TAVI delivery system enter his/her body. The anticipated dropout rate for this study population is expected to be low, as part of the selection criteria is subject compliance with all follow-up visits. Subjects that withdraw from the investigation or are lost to follow-up will not be replaced in the analysis dataset.

It is anticipated that there may be subjects who are enrolled in the study but are not included in the analysis population. There may be subjects who gave consent to participate in the study but did not satisfy the baseline inclusion exclusion criteria, these are considered screen failures. There may also be subjects who have enrolled in the study and started the procedure, but do not have the SJM TAVI delivery system enter his/her body and are procedural exclusions due to their anatomy, circumstances related to the procedure, or physician judgment; these are considered to be procedural exclusion subjects. Screen failure subjects and procedurally excluded subjects will not be part of the analysis population.

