## Clinical Investigational Plan

Informed Consent Form and Data Protection Form are obtained and study eligibility is confirmed, subject data will be reviewed by the Subject Selection Committee prior to the implant procedure to confirm, risk assessment, echo and CT measurements. CT Imaging, will be reviewed to ensure acceptable annular measurements for the Portico Transcatheter Heart Valve.

The Subject Selection Committee's decision on whether to include the subject in the study must be documented and communicated to the enrolling site by the Sponsor. If the Subject Selection Committee considers the subject ineligible for implant, the subject will be withdrawn from the study and the reason for exclusion documented.

The membership and process is further defined in the Subject Selection Committee Charter.

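### The section 14 termination table counts enrolled (consented) subjects, but its probabilities assume n subjects at risk; read literally, the rule is less sensitive to harm than stated

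*Combined protocol and SAP*

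**What the plan says.** Section 14.0 sets the termination criterion as the number of events x for which the chance of x or more is below 0.05, under a binomial model with event probability 0.119. The table gives x = 6, 8 and 9 at n = 20, 30 and 40, with probabilities 0.0251, 0.0211 and 0.0423. The column for n is headed "Number enrolled (n". Section 14 does not define n any further.

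Enrolment is defined twice. Section 5.3: "Subjects are considered enrolled in the study from the moment the subject has provided written Patient Informed Consent". Section 6.2.1.2 says that subjects who have received the information sheet and "signed an Informed Consent Form and Data Protection Form will be considered enrolled in the study".

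The plan expects some enrolled subjects never to receive the device:

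- Section 6.2.1.2: "It is anticipated that there may be subjects who are enrolled in the study but are not included in the analysis population". The analysis population is restricted to those who also "had the SJM TAVI delivery system enter his/her body", and "Screen failure subjects and procedurally excluded subjects will not be part of the analysis population".
- Section 7.2, where committee review follows consent: "If the Subject Selection Committee considers the subject ineligible for implant, the subject will be withdrawn from the study".
- Section 5.7.4: "Any subject that does not have a delivery system enter his or her body will be withdrawn from the study".

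Section 5.6 lists consent among the baseline activities and allows the baseline visit up to 30 days before the index procedure. At any look, some consented subjects may therefore still be waiting.

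**The concern.** A binomial tail with n trials is right only if each of the n subjects can have the event. The reference rate of 0.119 is a 30-day rate in patients who had a transcatheter valve procedure (section 6.3). A subject who fails screening, is refused by the committee or has not yet been treated cannot have a major vascular complication of that procedure, yet counts in n as labelled. The primary endpoint is divided by a treated population (sections 6.2.1.1 and 6.2.1.2), so the stopping rule and the endpoint it protects would use different denominators.

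What is at stake is sensitivity. Section 6.8 says there are no statistical criteria for termination, so this table is the study's only numerical safety limit. If n runs ahead of the number at risk, reaching x events requires a higher complication rate among those actually treated.

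**Working it through.** **Inputs.** From section 14: p0 = 0.119; (n, x) = (20, 6), (30, 8), (40, 9); criterion P(X ≥ x) < 0.05. From section 6.3: 23.3%, the highest rate in the cited meta-analysis, used here as an example of an elevated true rate. Assumed: f, the share of enrolled subjects at a look whose procedure has not been started. The documents give no value, so f is varied from 0 to 30%.

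**1. Reproduce the table.** P(X ≥ x) = 1 − Σ(k = 0 to x−1) C(n,k) 0.119^k 0.881^(n−k). With all n at risk this gives 0.02506, 0.02106 and 0.04233, which match the printed values. Each x is the smallest that qualifies, because x−1 gives 0.0804, 0.0584 and 0.0960. The arithmetic is correct when n means subjects at risk.

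**2. Replace n by the number at risk.** Put m = n(1 − f), rounded, and keep x as printed. (For f = 5% and n = 30, m = 28.5 is taken as 28.) For example, with f = 20% and n = 20, m = 16 and P(X ≥ 6 | 16, 0.119) = 0.0079.

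**3. Chance of crossing by n = 40.** This is the exact probability of reaching x at any of the three looks, with events carried forward, at a true rate of 23.3% among those at risk.

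| Assumed f | At risk at n = 20/30/40 | Tail at 0.119 | Crossing by n = 40 at 23.3% |
|---|---|---|---|
| 0% | 20/30/40 | 0.0251/0.0211/0.0423 | 64% |
| 5% | 19/28/38 | 0.0195/0.0139/0.0313 | 57% |
| 10% | 18/27/36 | 0.0148/0.0110/0.0224 | 50% |
| 20% | 16/24/32 | 0.0079/0.0051/0.0103 | 35% |
| 30% | 14/21/28 | 0.0036/0.0019/0.0039 | 21% |

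**4. Does the printed x still follow from the stated rule?** With f = 20%, the smallest x with a tail below 0.05 is 5, 7 and 8 for 16, 24 and 32 at risk (tails 0.0337, 0.0186, 0.0306), not 6, 8 and 9. The observed rate needed to trigger rises from 6/20 = 30.0%, 8/30 = 26.7% and 9/40 = 22.5% to 6/16 = 37.5%, 8/24 = 33.3% and 9/32 = 28.1%.

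**The case against.** The strongest reply is that n was meant as treated subjects and only the label is loose. There is support for this. Section 6.3 caps what a centre may enroll at 23, half of a sample size that section 4.2 counts in subjects undergoing valve replacement. Appendix G places the frailty assessment before enrolment but after consent. The printed probabilities are exact for subjects at risk, and the table stops just short of 45. The intention may well have been treated subjects. Even so, both formal definitions say consent and section 14 does not depart from them, so whoever applies the rule has to guess.

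Four stronger readings are tempting, and the documents do not support them.

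- A reader might infer that the rule breaches its own criterion. It does not: dilution lowers the tail, so each look stays below 0.05. The fault lies in sensitivity, not in excess stopping.
- A reader might infer that no subject outside the analysis population can have an event. That is true of screen failures, committee refusals and those awaiting treatment. It is not true of procedural exclusions: section 6.2.1.2 describes them as having started the procedure, section 5.7.4 collects possible adverse events on them, and the Appendix D definition covers access-related injury that can precede entry of the delivery system.
- A reader might infer that a large loss is established. It is not. Section 5.2 has sites check eligibility before asking for consent, so a small untreated share is plausible.
- A reader might infer that harm would go undetected. Section 14 also lets the sponsor suspend on suspicion of unacceptable risk and terminate at any stage, and section 9.2 requires vascular complications to be reported within 72 hours. These safeguards remain, but they do not correct the one numerical limit.

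**Conclusion.** The concern holds as a mismatch between the label on n and the model behind the probabilities. Under the plan's own definition of enrolment, the table is exact only if every enrolled subject has started the procedure by the time of the look. Otherwise the boundary is harder to reach than stated. The direction is certain; the size is not, because it depends on an untreated share that the documents do not give. Across the assumed 0 to 30%, the chance of crossing by n = 40 at a true 23.3% runs from about 64% down to 21%; at 5% the loss is about 7 percentage points. These figures take subjects not yet started as having no risk and all others as having the full 30-day risk. The point deserves correction because it concerns a decision threshold and is cheap to settle.

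**What to change.** Relabel the column in section 14 as the number of subjects in whom the index procedure was started. Add a sentence saying that the criterion is met as soon as x major vascular complications through 30 days have occurred among those n subjects. The x values and probabilities then stand as printed.

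An alternative is to use the section 6.2.1.2 analysis population, provided that any major vascular complication in a procedural exclusion still counts as an event and that subject is included in n. Without that proviso, an injury during a failed access attempt would drop out of the safety count, which matters in a study of access routes. Counting every subject whose procedure was started is cleaner because it treats everyone at risk in the same way.

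The cost is one heading and one sentence, made through a CIP amendment. There is a small downside: each look comes slightly later in calendar time than a count of consents would give.

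Separately, section 14 sets the criterion on complications over both arms together, then says that the arm not under suspension continues. The sponsor must reconcile whether n and x are pooled or per arm. The relabelling does not settle that question and should not be worded as if it did.
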